8.2.2.7 Serious Adverse Events Require Immediate Reporting

In the event of an SAE, whether associated with study drug or not, the investigator will notify Clinical Pharmacovigilance within 24 hours of the site being made aware of the SAE by entering the SAE data into the electronic data capture (EDC) system. SAEs that occur prior to the site having access to the RAVE[®] system, or if RAVE is not operable, should be documented on the

SAE Non-CRF forms and emailed (preferred route) or faxed to Clinical Pharmacovigilance within 24 hours of the site being made aware of the SAE.

Email (preferred):	[REDACTED]
	and
	[REDACTED]
Fax:	[REDACTED]

For general or specific patient safety concerns, please contact the Medical Director listed below:

[REDACTED]

[REDACTED]

In emergency situations involving study subjects when the primary Therapeutic Area Medical Director (TA MD) is not available by phone, please contact the 24-hour AbbVie Medical Escalation Hotline where your call will be re-directed to a designated backup AbbVie TA MD:

Phone:	[REDACTED]
---------------	------------

8.3 Toxicity Management

Subjects will be monitored continuously for toxicity while on study treatment. Toxicity will be assessed using the NCI CTCAE Version 4.03. Adjustments to these guidelines may occur based on the clinical judgment of the investigator with notification to the TA MD.

8.3.1 Management of Serosal Effusions/Serositis

Serosal effusions (pleural or pericardial, or ascites) have been observed with rovalpituzumab tesirine, and have the potential to be life-threatening (e.g. pericardial tamponade). Therefore, development of any of these events or worsening from baseline warrants prompt evaluation by the investigator or designee. Alternative causes, such as infection, congestive heart failure, disease progression, and in particular an immune-mediated AE (as might be caused by a checkpoint inhibitor; see Section 8.3.3), should be ruled out. When appropriate, a unifying

diagnosis should be reported, e.g. "heart failure," not simply "pleural effusion" and "edema limbs."

When considered clinically significant (e.g. grade 2 or higher and considered related to study drug):

- Systemic corticosteroids, when initiated promptly, have been reported to be beneficial in some prior cases during treatment with rovalpituzumab tesirine. The investigator should consider initiation of prednisone 1-2 mg/kg/day or equivalent, initiating a taper after improvement to Grade 1 or less, over the following 2-4 weeks.
- Until clinical experience suggests otherwise, guidance for dose delay and/or reduction of rovalpituzumab tesirine, as well as criteria for ongoing dosing, should follow Section 5.2.3 and Section 5.5.

8.3.2 Management of Skin Reactions

Skin reactions have been described during single-agent treatment with rovalpituzumab tesirine, nivolumab and ipilimumab. For rovalpituzumab tesirine, these have consisted primarily of photosensitivity, although other reactions such as palmar-plantar erythrodysesthesia and erythema multiforme have been reported. In contrast, for nivolumab and ipilimumab, immune-mediated dermatitis or rash has been described (Section 8.3.3 and Appendix 13.7). As such, development of a skin reaction during treatment warrants prompt evaluation by the investigator or designee:

- If clinically consistent with photosensitivity, the AE may be reported as such (using medically accurate and descriptive AE terminology), and managed as described in Table 5.
- If not clinically consistent with photosensitivity, the following should be done:
 - Photo documentation to facilitate later review by the sponsor or designee.
 - Formal evaluation by a dermatologist, including possible skin biopsy, to rule out alternative etiologies, such as erythema multiforme which may warrant discontinuation of study drug(s), and to facilitate the most appropriate terminology for AE reporting.
 - Immune-mediated skin reactions should consider the guidance of Appendix 13.7.

Table 5. Recommended Management of Photosensitivity

CTCAE v4.03		Treatment Recommendations	Dose Modifications
Grade 1	Painless erythema and erythema covering <10% body surface area (BSA)	Low-potency topical steroid (face) High-potency topical steroid (body)	–
Grade 2	Tender erythema covering 10–30% BSA	Low-potency topical steroid (face) High-potency topical steroid (body) Nonsteroidal anti-inflammatory agents orally as needed	–
Grade 3	Erythema covering >30% BSA and erythema with blistering; photosensitivity; oral corticosteroid therapy indicated; pain control indicated (e.g., narcotics or NSAIDs)	Low-potency topical steroid (face) High-potency topical steroid (body) Prednisone 0.5 mg/kg x 7 days	Reduce dose
Grade 4	Life-threatening consequences; urgent intervention indicated	Low-potency topical steroid (face) High-potency topical steroid (body) Prednisone 0.5 mg/kg x 7 days Hospitalization	Reduce dose

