5.5 Dose Delays/Modifications (Nivolumab and Ipilimumab)

5.5.1 Dose Delay Criteria (Nivolumab and Ipilimumab)

Dose reductions for nivolumab and ipilimumab are not permitted in this study. Nivolumab monotherapy or both nivolumab together with combination therapy should be delayed for the following:

- Any Grade ≥ 1 pneumonitis
- Any Grade ≥ 2 non-skin, drug-related AE, with the following exceptions:
 - Grade 2 drug-related fatigue or laboratory abnormalities do not require a treatment delay.
- Grade 2 drug-related creatinine, AST, ALT, or total bilirubin abnormalities
- Any Grade ≥ 3 skin drug-related AE
- Any Grade 3 drug-related laboratory abnormality with the following exceptions:
 - Grade 3 or 4 lymphopenia does not require a dose delay
 - Any Grade 3 drug-related amylase and/or lipase abnormality that is not associated with symptoms or clinical manifestations of pancreatitis does not require dose delay.

Any AE, laboratory abnormality or inter-current illness which, in the judgment of the investigator, warrants delaying the dose of study medication. In the event of isolated CNS progression during study treatment, study drug(s) may be withheld while palliative treatment is administered, e.g. a standard course of whole brain radiotherapy in accordance with institutional practice, and restarted within 1 week after completion of radiotherapy. During this time the subject should be fully evaluated for other sites of disease progression. If more than 6 weeks have elapsed since the previous dose of study drug(s), the subject should undergo a radiographic tumor assessment before restarting study drugs. If additional sites of PD are present, the subject

will be required to discontinue study drugs (but may be eligible for re-treatment as per Section 3.1.2).

If the decision is made to resume nivolumab and/or ipilimumab dosing, the subject should restart treatment on the next regularly scheduled dosing visit. Skipped doses are not to be replaced. If treatment is delayed >6 weeks, the subject must be permanently discontinued from all study therapy, except as specified in Dose Discontinuation Criteria. Tumor assessments for all subjects should continue as per protocol **even if dosing is delayed**.

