5.5.2 Criteria to Resume Nivolumab/Ipilimumab Dosing

Subjects will be permitted to resume therapy at the same dose level(s) following resolution of the AE to \leq Grade 1 or to baseline within 6 weeks after the last dose, with the exception of subjects who meet criteria for permanent discontinuation as specified in Section 5.5.4 (Dose discontinuation criteria below). Subjects who meet criteria for permanent discontinuation must not receive further study therapy.

Subjects may resume treatment with nivolumab and/or ipilimumab when the drug-related AE(s) resolve(s) to Grade \leq 1 or baseline, with the following exceptions:

- Subjects may resume treatment in the presence of Grade 2 fatigue.
- For subjects with Grade 2 AST, ALT, or total bilirubin elevations, dosing may resume when laboratory values return to baseline and management with corticosteroids, if needed, is complete.
- Subjects with combined Grade 2 AST/ALT AND total bilirubin values meeting discontinuation parameters (Section 5.5.4) should have treatment permanently discontinued.
- Drug-related pulmonary toxicity, diarrhea, or colitis must have resolved to baseline before treatment is resumed. Subjects with persistent Grade 1 pneumonitis after completion of a steroid taper over at least 1 month may be eligible for re-treatment if discussed with and approved by the sponsor and/or medical monitor.
- Drug-related endocrinopathies adequately controlled with only physiologic hormone replacement may resume treatment after consultation with the sponsor and/or medical monitor.
- Dose delay of nivolumab or ipilimumab that results in treatment interruption of >6 weeks requires treatment discontinuation, with exceptions as noted in Section 5.5.4. However, if the toxicity resolves to \leq Grade 1 or baseline >6 weeks after the last dose, but the subject does not otherwise meet the criteria for permanent discontinuation (Section 5.5.4), and the investigator

believes that the subject is deriving clinical benefit, then the subject may be eligible to resume the study drug(s) following the approval of the sponsor and/or medical monitor.

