5.5.4 Permanent Treatment Discontinuation Criteria

Subjects meeting any of the following criteria will be required to permanently discontinue all assigned study drug(s).

- PD (see details regarding continuing treatment beyond initial assessment of progression per RECIST v1. 1). See Section 7.2.1 for additional details.
- Clinical deterioration, as assessed by the investigator
- Any Grade 2 drug-related uveitis or eye pain or blurred vision that does not respond to topical therapy and does not improve to Grade 1 severity within 6 weeks OR requires systemic treatment
- Any Grade ≥ 2 drug-related pneumonitis or interstitial lung disease that does not resolve following dose delay and systemic steroids (also see Pulmonary Adverse Event Management Algorithm);
- Any Grade 3 non-skin, drug-related AE lasting >7 days or recurs, with the following exceptions:
 - Grade 3 drug-related uveitis, pneumonitis, bronchospasm, hypersensitivity reaction, or infusion reaction of any duration requires discontinuation

- Grade 3 drug-related endocrinopathies adequately controlled with only physiologic hormone replacement do not require discontinuation
- Grade 3 drug-related laboratory abnormalities do not require treatment discontinuation except:
 - Grade 3 drug-related thrombocytopenia >7 days or associated with bleeding requires discontinuation
 - Grade ≥ 3 drug-related AST, ALT or Total Bilirubin requires discontinuation
 - In most cases of Grade 3 AST or ALT elevation, study drug(s) will be permanently discontinued. If the investigator determines a possible favorable benefit/risk ratio that warrants continuation of study drug(s), a discussion between the investigator and the Medical Monitor/designee must occur
- Any Grade 4 drug-related AE or laboratory abnormality (including but not limited to creatinine, AST, ALT, or Total Bilirubin), except for the following events which do not require discontinuation:
 - Grade 4 neutropenia ≤ 7 days
 - Grade 4 lymphopenia or leukopenia
 - Isolated Grade 4 amylase and/or lipase abnormalities that are not associated with symptoms or clinical manifestations of pancreatitis
 - Isolated Grade 4 electrolyte imbalances/abnormalities that are not associated with clinical sequelae and are corrected with supplementation/appropriate management within 72 hours of their onset

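### Table 5 advises dose reduction after Grade 4 photosensitivity, an event for which Section 5.5.4 requires stopping all study drugs

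*Combined protocol and SAP*

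**What the plan says.** Section 8.3.2 sends events that look like photosensitivity to Table 5. Its Grade 4 row covers life-threatening events that need urgent intervention. Across the treatment and dose-modification columns, that row ends: "Prednisone 0.5 mg/kg x 7 days Hospitalization Reduce dose". The Grade 3 row also calls for a reduced dose. The same section says of skin reactions: "For rovalpituzumab tesirine, these have consisted primarily of photosensitivity".

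Section 5.5.4 opens: "Subjects meeting any of the following criteria will be required to permanently discontinue all assigned study drug(s". One of its criteria is "Any Grade 4 drug-related AE or laboratory abnormality", qualified by "except for the following events which do not require discontinuation". Four exceptions follow:
- neutropenia of 7 days or less;
- lymphopenia or leukopenia;
- isolated amylase or lipase abnormalities without pancreatitis;
- isolated electrolyte abnormalities corrected within 72 hours.

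The general Grade 3 criterion in the same list is narrower: "Any Grade 3 non-skin, drug-related AE lasting >7 days or recurs".

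Two other provisions bear on the point. Section 5.5.1 states: "Dose reductions for nivolumab and ipilimumab are not permitted in this study". Section 5.5.2 states: "Subjects who meet criteria for permanent discontinuation must not receive further study therapy".

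**The concern.** A site managing Grade 4 photosensitivity finds one instruction in the skin-toxicity table and the opposite one in the discontinuation rules. Section 8.3.2 does not refer to 5.5.4 for photosensitivity, and neither section says which prevails. By contrast, Section 8.3.1, on serosal effusions, does point the reader to Section 5.5 for dosing.

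What is at stake is the second rovalpituzumab tesirine dose, planned for Cycle 3 Day 1 (Week 7). A site following Table 5 could give it at 0.2 or 0.1 mg/kg instead of 0.3 mg/kg to a subject who has had a life-threatening drug reaction and must stop all study drugs. Table 5 is also silent on nivolumab and ipilimumab, which 5.5.4 would stop as well.

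**Working it through.** The main check is a comparison of texts; the arithmetic serves only to size the problem.

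**Step 1. Which drug can the cell mean?** Section 5.5.1 rules out reducing nivolumab or ipilimumab. That leaves rovalpituzumab tesirine, whose lower levels are 0.2 and 0.1 mg/kg (Section 3.1). A reduction means giving it again.

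**Step 2. Does 5.5.4 catch the event?** Its Grade 4 criterion applies to drug-related events. Table 5 responds to photosensitivity by lowering the dose, and Section 8.3.2 describes photosensitivity as the main skin reaction to rovalpituzumab tesirine. The events that the table addresses are therefore in practice drug-related. None of the four exceptions is a skin event, so the criterion applies and the stop is mandatory.

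**Step 3. Is the Grade 3 row also in conflict?** No. The general Grade 3 stop rule is limited to non-skin events, so reducing the dose for Grade 3 photosensitivity is compatible with 5.5.4. Within Table 5 the conflict is confined to the Grade 4 cell.

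**Step 4. Can 5.5.3 be reconciled with 5.5.4?** Section 5.5.3 makes reduction of rovalpituzumab tesirine the general course after a clinically significant Grade 3 or 4 event. Its wording is advisory and leaves room for the mandatory rule. Read that way, it still governs Grade 3 events that 5.5.4 does not stop and the excepted Grade 4 events. The Table 5 Grade 4 cell has no such remaining scope: a drug-related event must stop treatment, and an unrelated event gives no reason to reduce the dose.

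**Step 5. How many subjects?** The nearest figure is the 8% of related Grade 3 or higher skin reactions, of all types, that Section 1.4 reports for rovalpituzumab tesirine. Section 1.4 also says that the combination had not been formally studied, so carrying the figure over is an assumption. The sample-size ceiling is 90 subjects, or 30 per cohort (Section 10.1).

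- All related Grade 3 or higher skin reactions: 0.08 × 90 = 7.2; 0.08 × 30 = 2.4.
- Let f be the share of these that is Grade 4 photosensitivity. The documents do not give f; 1%, 5% and 10% are assumed.
- Expected number = 0.08 × f × N.

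| f (assumed) | 0.08 × f | N = 90 | N = 30 |
|---|---|---|---|
| 0.01 | 0.0008 | 0.072 | 0.024 |
| 0.05 | 0.004 | 0.36 | 0.12 |
| 0.10 | 0.008 | 0.72 | 0.24 |

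For a given f, these are expected events at any time on study and so an upper limit on wrongful redosing. For redosing, the event must come before Cycle 3, must resolve to Grade 0 or 1 or to baseline (Section 5.2.3), and must be handled under Table 5 rather than 5.5.4.

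**The case against.** The strongest objection is that the fault lies elsewhere. Section 5.5.3 is the rule specific to rovalpituzumab tesirine, and Table 5 repeats it. Section 5.5.3 goes on to stop the drug if the Grade 3 or 4 event recurs after a reduction, which presupposes that some Grade 4 subjects are redosed. On this view the real tension is between 5.5.3 and 5.5.4, and photosensitivity is one instance. It stands that 5.5.3 states no precedence and needs a clarifying clause. It does not rescue the Table 5 cell, for the reason in step 4.

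A second objection is that 5.5.4 may be meant only for the checkpoint inhibitors. The parent heading of Section 5.5 names only nivolumab and ipilimumab, and several criteria, such as uveitis, pneumonitis and endocrinopathy, suit those drugs. Section 5.5.2 is likewise titled for those two, so its sentence adds little about rovalpituzumab tesirine. The text nevertheless favours the wider reading:
- 5.5.4 speaks of all assigned study drugs, and names nivolumab or ipilimumab where it means only them, as in its dosing-delay criterion.
- 5.5.3 sits under the same parent heading and governs rovalpituzumab tesirine.
- 8.3.1 sends rovalpituzumab tesirine dosing questions to Section 5.5.

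What remains is that the sponsor's intention is inferred.

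A third objection is that the event is rare and safeguards exist. Table 5 is headed as recommended management, and Section 8.3 allows adjustment with notification. Section 5.5.4 separately stops subjects whom the investigator judges to be at substantial clinical risk. Hospitalization makes the event a serious adverse event, reportable within 24 hours. A drug-related Grade 4 non-laboratory event of this kind before Week 7 would also fall within the 12-week dose-limiting toxicity window of Section 3.1.1. All of this is true and makes unnoticed redosing unlikely. None of it corrects a cell that points the wrong way.

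**Conclusion.** The concern holds. For drug-related Grade 4 photosensitivity, Table 5 advises giving rovalpituzumab tesirine again at a lower dose, while 5.5.4 requires all study drugs to stop. That the texts conflict is certain. That Table 5 is the text in error is the better reading, and it rests on taking the scope stated in 5.5.4 at its word.

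The practical size is small: probably fewer than one affected subject in the trial, on the assumed shares above and on the 8% figure carrying over to the combination. At most one planned rovalpituzumab tesirine dose per affected subject is at stake. No endpoint, sample size or analysis is affected. It should still be corrected, because it concerns redosing after a life-threatening reaction.

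**What to change.** Change the Table 5 Grade 4 dose-modification cell to permanent discontinuation per Section 5.5.4, and leave the Grade 3 cell as it is. Open the last paragraph of 5.5.3 with a clause making it subject to any permanent discontinuation that 5.5.4 requires.

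If the sponsor in fact intends 5.5.4 to govern only nivolumab and ipilimumab, correct its opening sentence to say so and keep the Table 5 cell. Until the sponsor states which is meant, sites should follow the mandatory stop as the safer reading.

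The main fix is one table cell and one clause in a wording amendment. It adds no patients, visits or procedures.

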8.3.3 Management of Potential Drug-Induced Liver Injury

Wherever possible, timely confirmation of initial liver-related laboratory abnormalities should occur prior to the reporting of a potential drug-induced liver injury (DILI) event. All occurrences of potential DILIs, meeting the defined criteria, must be reported as SAEs.

Potential DILI is defined as:

- ALT or AST elevation >3 times (3 x) ULN; **and**
- Total bilirubin >2 times (2 x) ULN, without initial findings of cholestasis (elevated serum alkaline phosphatase), **and**
- No other immediately apparent possible causes of aminotransferase (AT) elevation and hyperbilirubinemia, including, but not limited to, viral hepatitis, pre-existing chronic or acute liver disease or tumor(s), or the administration of other drug(s) known to be hepatotoxic

In general, an increase of AT to >3 x ULN should be followed by repeat testing within 48-72 hours of all four of the usual measures (ALT, AST, alkaline phosphatase, total bilirubin) to confirm the abnormalities and to determine if they are increasing or decreasing. Inquiry regarding symptoms should also be made (e.g., fatigue, nausea, vomiting, right upper quadrant pain or tenderness, fever, rash). Subjects may be retested locally, but normal laboratory ranges should be recorded and results made to the investigator immediately. All data must be recorded in the eCRF. If symptoms persist or repeat testing shows AT >3 x ULN for subjects with normal baseline measures or 2-fold increases above baseline values for subjects with elevated values

before drug exposure, close observation should be initiated. If close monitoring is not possible, study drugs should be discontinued.

Close observation includes:

- Repeating liver enzyme and serum bilirubin tests two or three times weekly. Frequency of retesting can decrease to once a week or less if abnormalities stabilize or the trial drug has been discontinued and the subject is asymptomatic.
- Obtaining a more detailed history of symptoms and prior or concurrent diseases.
- Obtaining a history of concomitant drug use (including nonprescription medications and herbal and dietary supplement preparations), alcohol use, recreational drug use, and special diets.
- Ruling out acute viral hepatitis types A, B, C, D, and E; autoimmune or alcoholic hepatitis; non-alcoholic steatohepatitis (NASH); hypoxic/ischemic hepatopathy; and biliary tract disease.
- Obtaining a history of exposure to environmental chemical agents.
- Obtaining additional tests to evaluate liver function, as appropriate (e.g., international normalized ratio [INR], direct bilirubin).
- Considering gastroenterology or hepatology consultations.

Discontinuation of study drugs should be considered if potential DILI is suspected and:

- ALT or AST >8 x ULN
- ALT or AST >5 x ULN for more than 2 weeks
- ALT or AST >3 x ULN and (TBL >2 x ULN or INR >1.5)
- ALT or AST >3 x ULN with the appearance of fatigue, nausea, vomiting, right upper quadrant pain or tenderness, fever, rash, and/or eosinophilia

All subjects showing possible DILI should be followed until all abnormalities return to normal or to the baseline state. Retreatment of subjects who develop possible DILI and have previously discontinued study drugs may only be permitted upon approval by the sponsor and medical monitor.

8.3.4 Immune-Mediated Adverse Events

General guidelines for immune-mediated AEs, which have been described during treatment with nivolumab and/or ipilimumab, but not (to date) with rovalpituzumab tesirine, may be found in Appendix 13.7.

General principles include that differential diagnoses should be diligently evaluated according to standard medical practice, and consultation with a medical or surgical specialist, especially prior to an invasive diagnostic or therapeutic procedure, is recommended. These evaluations, in addition to the guidelines of Appendix 13.7 may be supplemented by discussions with the medical monitor. Non-inflammatory etiologies should be considered and appropriately treated.

